7. BACKGROUND AND SIGNIFICANCE

Clinical:

Approximately 517,000 infants are born prematurely every year¹, and as low birth weight and premature infants are surviving longer, they are at high risk of developing severe ROP. In the United States, 2,000 infants per year are diagnosed with severe ROP, which is the leading cause of irreversible childhood blindness in the United States. In our NICU, we care for between 60 and 80 infants each year that are born with low birth weight.

Usual parenteral nutrition protocols do not meet the infants' fetal accretion rates. Despite receiving 14-28 mg DHA/kg/day,² preterm infants have lower serum DHA and EPA levels than they would have had *in utero*, and

their tissues have lower n-3 and n-6 fatty acid than full term infants, indicating that their dietary needs are often not met.³ Preterm and small for gestational age infants have altered serum phospholipid fatty acid profiles with lower DHA and polyunsaturated omega-3 fatty acids than appropriate for gestational age infants.⁴ Low birth weight infants often have severe lung disease and are exposed to exogenous oxygen, which causes retinal blood vessel attenuation, retinal hypoxia, up regulation of pro-angiogenic factors, and neovascularization, which can lead to irreversible vision loss.

In a recent Polish prospective interventional study, Pawlik et al. showed that in preterm infants (average 28 week gestation, 935 gram birth weight), continuous intravenous n-3 fatty acids with Omegaven® from day one to day 28 of life, followed by enteral omega-3 fatty acids is safe and resulted in a significantly decreased need for ROP laser treatment. In the treatment group, 9 of 60 infants needed laser compared with 22 of 70 infants in the control group.^{7,12} On treatment, infants had higher plasma and red blood cell DHA levels at 7 and 14 days and a lower risk for cholestasis. This study showed that treatment was well tolerated in preterm infants and that Omegaven® has a positive effect on ROP pathogenesis, but no investigations were done into the mechanisms by which ROP was suppressed in the experimental group compared with the control arm. There is also no clinical data that currently differentiates the differences in the blood biology (fatty acids, gene expression, and proteins) in infants with and without severe ROP.

Translational:

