Fatty acid supplementation will continue until the baby is full term (40 adjusted weeks of age). If the infant is discharged before he/she is full-term, the infant will be sent home with a bottle of the fatty acid oral solution for the infant to continue daily until he/she is full-term (40 weeks of age). The infant's nutritional needs will be carefully monitored by his/her doctor and nutritionist per NICU protocols.

To monitor the amount of fatty acid nutrition getting into the blood, we will check the infant's blood. As much as possible, we will coordinate the study blood collection at the same time as the routine NICU blood draws. We will collect 1.3 milliliters of blood at 4 different times spread apart while the infant is in the hospital. At each time point, we will collect about 1/4 teaspoon of blood, for a total of about 1 teaspoonful.

The blood draws will occur as the following four time points:

- Blood draw T0= Prior to parenteral nutrition, within 1st 3 days of life. This blood collection should be

taken from cord blood. If cord blood is not available, sample will be collected from a UAC, UVC, or peripheral blood draw concurrent with SOC.

- Blood draw T1= 5 days after parenteral nutrition is started; grace period +/-3 days therefore total 2-8 days after parenteral nutrition started.
- Blood draw T2= 5 days after enteral nutrition full feeds have arrived; grace period +/-3 days therefore total 2-8 days after full enteral nutrition arrived.
- Blood draw T3= Prior to discharge from hospital coinciding with time that ROP may be present, ≥ 35 weeks adjusted age.

This blood will be used for looking at what new genes (mRNA) the infant is making and to check how many and what kind of fatty acids the infant has in the blood. Before testing, the blood will be stored in a storage facility at the UCSD Department of Ophthalmology Blood Bank and labelled with a barcode without the infants' personal information. This is not the infant's DNA, and no DNA will be isolated or tested. Samples will be stored for 10 years. After this time point, all samples will be destroyed if not used by that time. If the parent decides to withdraw consent the blood samples that were already drawn will be destroyed, however, any previously obtained data from sample testing will be kept.

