Eye exams: All infants will get eye exams according to standard NICU protocols. Serial eye exams will be performed according to the usual intervals, which is until retinal vascularization has matured or active ROP has stabilized, usually at 1-2 months post-term. The area of vascularized retina, clock hours of neovascularization, and amount of retinal vascular dilation and tortuosity will be measured by indirect ophthalmoscopy in all infants at each clinical exam by an ophthalmologist masked to the treatment group. Stage of retinopathy of prematurity and need for ROP treatments will be measured at 40 weeks gestation plus or minus three weeks and followed over time. Infants with ROP will be monitored over time for longer term visual and anatomic outcomes. For both groups, infants will have SOC eye examinations prior to discharge around 40 weeks GA (≥ 38 wks GA). For both groups, if infant is discharged prior to 38 weeks GA, we will collect follow-up data from their outpatient follow-up eye exam from UCSD or other provider

Nutrition: Omegaven has been approved by the FDA for use in children and infants with parenteral nutrition associated liver disease (PNALD). In this study we intend to use Omegaven under an IND exemption to study the use of the drug in reducing the incidence and severity of retinopathy of prematurity (ROP). Our aim is to differentiate the phospholipid profiles and gene expression pathways of at-risk very low birth weight infants with and without treatment with Omegaven® (high n-3 fish oil supplement) and to establish whether omega-3 fatty acid supplementation in extremely low birth weight infants will reduce the incidence and severity of retinopathy of prematurity (ROP). The study intervention “drug product” has been used in the neonatal population via the same route of administration safely for other disease indications internationally and nationally including here at University of California San Diego. This investigation does not significantly increase the risk or decrease the acceptability of risk of our study population.

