Once enteral nutrition reaches desired minimum mL/kg/day (determined by the NICU neonatology team), then parenteral supplementation will be discontinued and enteral supplementation will begin. Carlson’s Fish oil ® (400 mg of omega 3 fatty acids: EPA 200 mg, DHA 125 mg, and 75 mg of other omega-3 fatty acids per ¼ tsp) will be given in the experimental group. Enteral fish oil supplementation of 1.25mL/kg/day (1/4 teaspoon per kg per day) divided at least every 12 hours for tolerance will be continued until the baby is at 40 weeks adjusted age or the retina is fully vascularized. We will adjust our fish oil dosage to maintain maximum enteral DHA supplementation to 125 mg/kg/day (omega3 400mg/kg/day). The total dose will be given BID initially. If there are any symptoms of GERD or other intolerance symptoms that are concerning to the primary team, then oral fish oil total daily dose will be divided over multiple administrations. If enteral oil is not tolerated even after medical management, we can decrease the amount by 25% until tolerated. We do not expect poor tolerance to this dose given 120 mg/kg/day has been tolerated as an emulsion via feeding tube without any complications²¹. As it is typical of this study population to require varying needs of care and drug administration, should any infant randomized to the Omegaven arm require discontinuation of the study drug for clinical reasons for more than

five days (either consecutive or accumulative), that infant will be withdrawn from the study. Drug administration disruptions occurring for 5 or less days (total) shall not be considered protocol deviations but will be recorded and noted in the annual FDA safety report.

Following discharge from the NICU and prior to infants reaching 40 wks, a research team member (other than the PI) will contact the parents with infants in the Omegaven arm once weekly to encourage parents to continue with the prescribe fish oil administration for their infant until he/she has is 40 weeks adjusted age.

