The investigational drug pharmacy (IDS) will obtain the Omegaven and dispense it to the nurse for administration in a separate line than the rest of the nutrition (amino acids, sugars, etc). The NICU nutritionist will optimize the total nutritional calories to the infant per NICU protocols. The IDS pharmacist, nutritionist, and NICU team will not be blinded to ensure that the infant in the Omegaven group meets all the nutritional requirements as determined by the NICU neonatology attendings and fellows involved in the study. The ophthalmology team will be blinded to the treatment group to prevent any potential for bias during the eye exam.

Outcome Measures:

Outcome 1: Change in concentrations of basic fatty acids (EPA, DHA, and AA) and their bioactive metabolites will be assessed at multiple time points.

Outcome 2: Change in mRNA expression of TNF- α , PPAR- γ , and VEGF at multiple time points.

Outcome 3: Severity stage of ROP in Group 1 compared to Group 2. This will be assessed at the time of ROP screening (approximately 31 weeks), and the outcome will be measured at approximately 40 weeks adjusted age. The stage of ROP at 40 weeks adjusted will be used for statistical analyses.

Safety:

A data safety monitoring board (DSMB) will be established to monitor the safety of enrolled infants in the study as well as identifying the efficacy of the treatment at ongoing intervals. The DSMB will meet after the first 5 infants are enrolled and then regularly at multiple intervals during the study. Clinical safety assessments will occur during the hospital admission including vital signs, weight, physical exam and laboratory assessments of triglycerides. The neonatologist will review the assessments and determine if the subject should remain in the study or be removed.

Statistical Analysis

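### The only planned test of the ROP aim uses a single stage at about 40 weeks, with no level for no ROP and no rule for treated or regressed eyes

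*Combined protocol and SAP*

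**What the plan says.** All references are to the combined protocol and SAP.

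- **Section 6, Specific Aims.** The second aim is to find out whether supplementation lowers both how often ROP occurs and how severe it is.
- **Section 9, Outcome Measures, Outcome 3.** ROP is assessed from screening at about 31 weeks, but "The stage of ROP at 40 weeks adjusted will be used for statistical analyses".
- **Section 9, Statistical Analysis, Outcome (c).** The model is a mixed-effects ordinal logistic regression. Its outcome is the stage after 40 weeks, with levels I to V. It takes over the terms of the DHA model: group, time, their interaction, and a random intercept and slope.
- **Section 9, Eye exams.** "Serial eye exams will be performed according to the usual intervals, which is until retinal vascularization has matured or active ROP has stabilized", which the text puts at usually one to two months past term. Stage is measured, and "need for ROP treatments will be measured at 40 weeks gestation plus or minus three weeks and followed over time".
- **Section 9, Nutrition.** Enteral supplementation runs "until the baby is at 40 weeks adjusted age or the retina is fully vascularized".
- **Section 7, Background.** In the motivating study, "9 of 60 infants needed laser compared with 22 of 70 infants in the control group".

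No section analyses the worst stage, the need for treatment, or any examination after the 40-week window. None says how a treated or regressed eye is to be scored.

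**The concern.** ROP is followed over many weeks, and what matters for severity is how bad it became and whether it needed treatment. One reading at a fixed age answers a different question, namely what is visible on that day. Disease that worsens afterwards is not counted. An eye that was treated or has regressed before the reading is graded on the remainder.

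The scale adds a second problem. With levels I to V only, an infant without ROP has nowhere to go, so the incidence half of the aim has no analysis.

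ROP prevention is in the trial's title and is its second aim, and the evidence that motivated the trial was a difference in laser treatment. That same outcome is collected here and then left out of the analysis. If severe cases are graded low and one arm has more of them, the observed group difference shrinks.

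**Working it through.** **1. The plan's own figure.** The only power statement concerns DHA: over 80% with 20 per group, difference 42 − 27 = 15, SD 15, two-sided 0.05. The standardised difference is 15/15 = 1. The normal approximation gives Φ(1 × √(20/2) − 1.96) = Φ(1.20) = 0.885, and the exact t-test gives 0.869. The statement reproduces. No power or sample size is given for ROP, and this point does not rest on the DHA figure.

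**2. Timing, from section 9.**

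| Event | Age in weeks |
|---|---|
| Screening starts | about 31 |
| Analysed stage (Outcome Measures) | 40 |
| Measurement window (Eye exams), 40 ± 3 | 37 to 43 |
| Usual maturity or stabilisation, 1 to 2 months after term (taking 4 weeks per month) | about 44 to 48 |

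The analysed reading comes 40 − 31 = 9 weeks after screening starts and about 4 to 8 weeks before disease usually settles. Even the wide window closes at 43 weeks, before that point. The documents state explicitly that examination continues past the reading. That treatment or resolution can come before it is implied, by the recording of treatment need around 40 weeks and by the alternative end of supplementation in the Nutrition text. Neither is dated.

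**3. Scale.** The levels are I, II, III, IV and V. An unaffected eye fits none of them. Nor does a fully regressed eye, so its score is undefined rather than simply low.

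**4. Model.** Time, group-by-time and random-slope terms need repeated values per infant. Outcome 3 supplies one. Outcome Measures says at 40 weeks and Statistical Analysis says after 40 weeks. These passages need reconciling.

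**5. Illustration of size.** Inputs from section 7:

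- Control: 22/70 = 31.4%. Treated: 9/60 = 15.0%. Difference: 16.4 points.
- Per 20 infants: 20 × 0.314 = 6.3 and 20 × 0.150 = 3.0, so about 9 of 40 infants would be open to misgrading.

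Let laser stand for severe disease. Let f be the share of laser-treated infants, equal in both arms, who no longer show their severe stage at the exam. The documents give no value for f, so the range is shown. Visible difference = (1 − f) × 16.4 points.

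| f | Control % | Treated % | Difference, points | Power, 20 per arm |
|---|---|---|---|---|
| 0 | 31.4 | 15.0 | 16.4 | 0.23 |
| 0.25 | 23.6 | 11.2 | 12.3 | 0.17 |
| 0.5 | 15.7 | 7.5 | 8.2 | 0.12 |
| 0.75 | 7.9 | 3.7 | 4.1 | 0.08 |
| 1 | 0 | 0 | 0 | – |

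Power is for a two-sided 0.05 comparison of two proportions (normal approximation, pooled variance under the null). With no misgrading at all, 80% power would need 103 infants per arm.

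**The case against.** The strongest reply is that DHA is the primary and only powered outcome, and that ROP inference is weak however it is defined: about 0.23 power at the cited laser difference with 20 per arm and perfect grading. That stands, and it limits how serious the point is. It does not make the endpoint suitable for the aim it serves.

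A second reply is that the time and random-slope terms show that repeated ROP data were meant. They may have been. But the outcome named in Statistical Analysis is the stage after 40 weeks, and Outcome Measures fixes one value. The most this shows is that the text is inconsistent.

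A third reply is that the size in the illustration is borrowed. It takes rates from another population, equates laser with severe stage and varies an unknown f. That also stands: it shows direction and range and is not an estimate.

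Four stronger readings are tempting, and the documents do not support them:

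- *The plan itself describes ROP as treated and resolved before 40 weeks.* It only implies that this can happen. The T3 blood draw is timed "Prior to discharge from hospital coinciding with time that ROP may be present", at 35 weeks or later, which is an open-ended sampling time and not a disease course.
- *The group difference could be reversed.* With equal f, (1 − f) × 16.4 never changes sign. Reversal at the cited rates needs unequal shares, with (1 − f) in controls below 15.0/31.4 = 0.48 of its value in the treated arm. Nothing in the documents suggests that.
- *Infants whose retina matures early leave the schedule before 40 weeks.* The Eye exams text provides an examination around 40 weeks for both groups, and follow-up data for infants discharged before 38 weeks.
- *The exam windows contradict one another throughout.* An exam at 38 weeks or later largely overlaps 40 ± 3 weeks. The clear mismatch is at versus after 40 weeks.

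**Conclusion.** The point holds for the second aim. Three parts follow directly from the text: one 40-week stage is the only ROP value analysed although examinations continue beyond it; need for treatment is recorded but unanalysed; and the scale has no level for no ROP, so incidence cannot be estimated. That a treated or regressed eye would be graded by what remains is a reasonable inference, but the documents give no timing for it.

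The likely consequence is attenuation. In the illustration the 16.4-point difference falls to anything between 16.4 and 0 points depending on f, assuming f is equal in both arms and laser marks severe disease. Missed progression after the exam is a further loss that the documents do not allow to be sized.

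This should be fixed, but it is not critical to the trial, because the DHA analysis and its power are untouched.

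**What to change.** In section 9, replace the Outcome 3 analysis sentence, and the outcome variable for Outcome (c), along these lines:

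- **Outcome.** The worst ROP stage in either eye at any examination from first screening to the last scheduled exam (retinal maturity or stabilisation). The ordinal scale starts at no ROP. Any infant who received ROP treatment is placed in the top category, whatever stage is seen later.
- **Model.** An ordinal model with one value per infant and a group effect. Drop the time, group-by-time and random-slope terms; a random intercept per infant has no repeated values to support it either.
- **Supporting outcomes.** The proportion of infants treated for ROP, and the stage at 40 weeks.
- **Timing.** One definition of the 40-week exam window, used alike in Eye exams, Outcome Measures and Statistical Analysis.

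The rule should be fixed before outcomes are compared by group, because choosing the worst stage or treatment afterwards would be post hoc.

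The cost is more than wording. Stage must be captured at every exam. The Eye exams text names other retinal measures at each exam, but lists stage only around 40 weeks and then followed over time. Some records after discharge must be collected up to one to two months past term. The Eye exams text and section 12 (Informed Consent) already provide for obtaining outside eye data, although Eye exams mentions this only for discharge before 38 weeks and the masking of outside examiners is not stated. No dose, schedule or treatment rule changes.

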We will examine the infant's eyes according to the standard NICU guidelines and protocols. We will also examine the infant's eyes in our eye clinic after discharge over time as we do for all premature infants to support the infant's visual development.

During the study:

Maternal diet questionnaires will be administered to the maternal subjects following enrollment. This questionnaire is the Omega 3 Fatty Acid Questionnaire and has been validated in a related study for this fatty acid¹⁹. It is anticipated to take 10-15mins to complete. Mothers will be asked to complete this questionnaire at the time of enrollment.

Blood samples will be collected 4 times. When possible, and in the majority of blood draws, 1.3 cc of whole blood will be collected at the same time as other blood draws to avoid multiple sticks. Whole blood will be collected in a green or lavender top tube. One hundred μ l of plasma will be isolated, and this will be aliquoted into in two tubes and frozen (-80°C).

Lipidomics: Plasma fatty acids will be tested using a preprandial whole-blood sample (1.3 mL) drawn 2-4 hours after the parenteral nutrition (PN) had ended for the day and after enteral feedings were held for 3 hours if the patient was also fed enterally. The schedule for sampling will be as follows: prior to parenteral nutrition within ≤ 3 days of life; within 5-8 days after parenteral nutrition is started; within 5-8 days after enteral nutrition full feeds is started; and prior to discharge from hospital coinciding with time that ROP may be present. The samples will be sent to [name] of Engineering in Medicine Laboratory at UCSD or another UCSD laboratory for internal validation of assays. [name] lab (UCSD Department of Ophthalmology) or another laboratory with similar capabilities will perform some of the RNA isolation and analysis. Capillary gas chromatography/mass spectroscopy will be the one of the main methods used to determine the phospholipid profile.

Transcriptomics: From the plasma isolated from the whole blood samples, 50 μ l will be used for mRNA isolation. This will be collected and frozen as the study is ongoing. The fold expression of genes associated with the fatty acid synthesis pathway, hypoxia and pro-angiogenic pathways will be correlated with clinical disease.

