15. RISK MANAGEMENT PROCEDURES AND ADEQUACY OF RESOURCES

Adequate measures have been taken to minimize all of the above risks prior to initiation of this study, including proper design specification and review, preclinical testing, and clinical evaluations. The study doctor will provide appropriate training to the research staff prior to our study initiation.

Safety assessments will include vital signs, weight, physical exam and safety laboratory assessments. The PI or sub-PIs will review the assessments and determine if the subject should remain in the study or be removed.

Loss of Confidentiality:

There is a risk of a loss of confidentiality if information on the study is lost or stolen. Every measure will be taken to ensure confidentiality. The chance of a loss of confidentiality occurring during this study is highly

unlikely. However, there is a potential risk of loss of confidentiality by participating in this study. Research records will be kept confidential to the extent provided by law. It is however, always possible that the information in the research records could become known outside of the research setting. To minimize this risk, all records which identify the subject will be stored in a locked file cabinet in a locked office and will only be accessible by study staff. Computers used to store subject's information are password-protected and only accessible by study staff.

A Data Safety Monitoring Board (DSMB) will be created. The function will be to monitor data regarding safety of the treatment in enrolled infants as well as identifying the efficacy of the treatment at ongoing intervals.

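### Fish oil continues at home, but no non-ocular adverse-event collection is described after discharge, and the weekly call that could supply it goes to one arm only

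*Combined protocol and SAP*

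**What the plan says.** Two places describe safety assessment. The Safety paragraph of section 9 ties it to the inpatient stay: "Clinical safety assessments will occur during the hospital admission including vital signs, weight, physical exam and laboratory assessments of triglycerides". Section 15 gives a similar list without naming a setting: "Safety assessments will include vital signs, weight, physical exam and safety laboratory assessments".

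Dosing goes on after the inpatient stay. For an infant discharged before term, section 9 says "the infant will be sent home with a bottle of the fatty acid oral solution for the infant to continue daily", up to 40 weeks adjusted age. The enteral paragraph under Nutrition gives the stopping point as 40 weeks or full vascularization of the retina.

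That same part of section 9 sets three further rules:
- **Weekly call.** After discharge and before 40 weeks, a research team member other than the principal investigator will "contact the parents with infants in the Omegaven arm once weekly to encourage parents to continue with the prescribe fish oil administration".
- **Tolerance steps.** Splitting or reducing the oil begins from this condition: "If there are any symptoms of GERD or other intolerance symptoms that are concerning to the primary team".
- **Interruptions.** In the Omegaven arm, breaks totalling five days or fewer are to be recorded and reported in the annual FDA safety report. More than five days off drug for clinical reasons, consecutive or cumulative, leads to withdrawal.

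Eye follow-up is separate and covers both arms. Section 9 plans to examine the infants' "eyes in our eye clinic after discharge over time as we do for all premature infants". For infants of either group discharged before 38 weeks, it collects data from the outpatient eye examination.

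**The concern.** A study product is given beyond the period for which safety assessment is stated, and the one non-ophthalmic contact in that later period differs by arm. Two problems follow.

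The first is coverage. The DSMB is asked to monitor safety in enrolled infants, and investigators may withdraw an infant for side effects (section 10). Neither can act on events at home that no procedure brings to them. The protocol itself anticipates reflux and intolerance, and section 18 calls the study risks more than minimal. Its reassurance on tolerance cites an emulsion given by feeding tube, which is a different setting from oil given by parents at home.

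The second is balance. The call is meant to support adherence, but parents may mention problems on it. Those reports would come only from the Omegaven arm, so a comparison of harms that used them would be tilted against that arm by the way they were collected. A comparison that left them out would have no home data at all.

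**Working it through.** The point rests mainly on setting the provisions side by side. The plan gives no figure for home exposure, so there is none to reproduce, and the power calculation does not bear on it.

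**Step 1: what each post-discharge provision collects**

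| Provision | Arms | What it is described as collecting |
|---|---|---|
| Safety paragraph, section 9 | Both | Assessments during the admission |
| Safety list, section 15 | Both | Similar items; no setting, no home schedule |
| Weekly call, section 9 | Omegaven only | Nothing stated; the purpose is to encourage dosing |
| Eye visits and outside eye data, section 9 | Both | Eye findings |
| Interruption record, section 9 | Omegaven only | Days off drug; no home source named |

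No row yields non-ocular adverse events at home. The interruption record and the five-day withdrawal count are complete only if days missed at home are known, and the call is not described as asking about them.

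**Step 2: length of the home period**

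Inputs: supplementation ends at 40 weeks adjusted age (section 9). Discharge age is not given, so 35 to 38 weeks is an assumption. The lower value comes from the last blood draw, taken before discharge at 35 weeks or later. The upper value comes from the eye-exam text, which treats discharge before 38 weeks as a separate case. Neither is a discharge age.

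Home period = 40 − discharge age:
- 35 weeks: 40 − 35 = 5 weeks
- 36 weeks: 40 − 36 = 4 weeks
- 37 weeks: 40 − 37 = 3 weeks
- 38 weeks: 40 − 38 = 2 weeks

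Later discharge shortens this further, to zero at 40 weeks. Full vascularization before 40 weeks would also shorten home dosing under the enteral paragraph.

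**Step 3: share of the course, as illustration only**

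Counting from birth to 40 weeks, an infant born at 30 weeks has a course of 40 − 30 = 10 weeks, and one born at 23 weeks has 40 − 23 = 17 weeks.
- Discharge at 35 weeks: 5/10 = 50% and 5/17 = 29%
- Discharge at 38 weeks: 2/10 = 20% and 2/17 = 12%

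**Step 4: size of the added work**

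With 60 infants split equally, the control arm has 60/2 = 30. If every control infant went home at 38 weeks, the added calls would number about 30 × 2 = 60 over the whole study. If every one went home at 35 weeks, they would number about 30 × 5 = 150.

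**The case against.** The strongest reply is that the plan does more after discharge than the Safety paragraph suggests, and several stronger readings fail for that reason.

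- A reader might infer that the weekly call is the only contact after discharge. It is not: eye follow-up is planned in both arms. This stands. However, those visits are described as gathering eye findings only, some come from outside providers, and the ophthalmology team is masked, so asking about oil tolerance there would risk unmasking.
- A reader might infer that harms at home go wholly unrecorded. That is too absolute. Eye outcomes are collected, section 15 does not limit safety assessment to the admission, and the DSMB's remit covers enrolled infants without restriction to inpatients. Still, section 15 schedules nothing at home, and a remit does not supply data.
- A reader might infer that missed doses at home are not to be recorded. Section 9 requires short interruptions to be recorded, with no inpatient limit. What is missing is a described way of learning about them.
- A reader might infer that infants at home have nobody overseeing tolerance. The documents do not show that. The primary team is undefined, and the sentence on monitoring by the infant's doctor and nutritionist directly follows the home-dosing sentence, so it may extend to the home. It refers to NICU protocols, however, and is not linked to study safety data.
- Consent pages are not part of the reviewed text, so instructions to parents on reporting symptoms cannot be presumed absent.

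It is also fair to say that the plan gives no adverse-event definitions, grading or reporting route for the hospital period. That widens the problem and does not answer this point.

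**Conclusion.** The point holds in a limited form. Safety assessment is stated for the admission, oil continues at home, no non-ocular adverse-event collection is described after discharge in either arm, and the one non-ophthalmic contact is made in one arm for adherence. Harms volunteered through it would be ascertained unequally, and the required record of interruptions has no stated home source.

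The home period is about 5 to 2 weeks if discharge falls at 35 to 38 weeks. That range is an assumption. The statement that half the course is unmonitored would need discharge at 35 weeks, birth at 30 weeks and no earlier stop for full vascularization; the documents do not establish this combination as typical.

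The planned DHA comparison does not depend on this point. What is incomplete is the comparative safety information, so the change should be made but does not put the primary analysis in doubt.

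**What to change.** 1. In the Safety paragraph of section 9 and in section 15, state that adverse-event collection runs to 40 weeks adjusted age in both arms. Say that this means event reports, not the in-hospital examinations or laboratory tests, which cannot be done by telephone.
2. In the enteral part of section 9, make the existing weekly call to parents in both arms, on the same schedule and with the same short fixed question set: feeding intolerance, vomiting or reflux, bleeding, readmission, death. Add missed oil days in the Omegaven arm, which gives the interruption record its home source.
3. Include the call records in the neonatologist's safety review and in the DSMB reports, and keep them from the masked ophthalmology team.
4. Reconcile the tolerance steps, which depend on an undefined primary team, with dosing at home. The clinical content is for the investigators to settle; this review proposes no rule.

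The cost is a call script and coordinator time for roughly 60 to 150 control-arm calls over the study under the assumptions above. A team member is already assigned to the Omegaven-arm calls. No extra visit or blood draw is needed.
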